**Table 8-1. List of analytical reports**

Reports	Main topic	Content/ Data cutoff	Report
Infant interim 1	Intention to breastfeed	Prenatal views/ Results through prenatal interview	1/11/2014
Infant interim 2	Initiation of breastfeed	Study design and sample Breastfeeding decisions Hospital practices and neonatal circumstances/ Result through 3 month interview	10/10/2014
Infant interim 3	Breastfeeding and formula supplementation	Knowledge attitudes , and sources of information (initial data) Breastfeeding problems Formula supplementation (initial data) Breastfeeding and formula feeding practices (initial data)/ Results through 7 month interview	2/13/2015

Table 8-1. List of analytical reports (continued)

Reports	Main topic	Content/ Data cutoff	Report
Infant interim 4	Infant Feeding Practices, Introduction to Solid Foods	Mother/Caregivers WIC experience (initial data) Continuation and cessation of breastfeeding Initiation of supplemental foods: the transition phase of infant feeding (initial data)/ Results through 13 month interview	8/14/2015
Infant final	1st Year Feeding Practices	All topics listed above (topics with initial data will be updated through 13 month interview )	10/9/2015
Toddler interim 1	Nutrient Intake & Weight Gain	Nutritional intake (initial data) Child's weight and feeding practices (initial data)/ Results through 15 month interview	10/9/2015
Toddler interim 2	Supplemental foods and feeding practices	Supplemental foods feeding practices(initial data)/ Results through 18month interview	1/8/2016
Toddler interim 3	Feeding practices, working and childcare	Feeding practices, working, and childcare (initial data)/ Results through 24 month interview	4/1/2016
Toddler interim 4	Nutrient Intake & Weight Gain	Nutritional intake Child's weight and feeding practices Results through 24 month interview	4/1/2106
Infant/Toddler final	1st & 2nd Year Feeding Practices	All topics (all topics with initial data will be updated through 24 month interview)	5/20/2016

# Appendix A

## Summary of WIC-IFPS-1 Analyses to be Repeated

Table A-1 provides a listed of all the tables and figures in the WIC-IFPS-1 final report in terms of the order in which they appear in the document. To facilitate cross-referencing to the WIC-IFPS-1 final report, we note the page on which the table or figure appears. We specify if we are repeating the analysis and note major deviations. In cases in which we will not repeat the analysis, we provide an explanation as to why.

**Table A-1. List of WIC-IFPS-1 report tables and figures**

Table/Figure	Page	Status
CHAPTER I: INTRODUCTION AND OVERVIEW		
This chapter contains no tables or figures		
CHAPTER II: STUDY DESIGN AND SAMPLE		
Table II.1 Overall study participation counts and rates	20	Will repeat
Table II.2 Counts and percent of respondents by sample type and interview month	21	Will repeat
Table II.3 Percentage distribution of socio-demographic characteristics by maternal race and ethnicity	25	Will repeat
Table II.4 Percentage distribution of reported health-related characteristics by maternal race and ethnicity of the mother	26	Will repeat
Table II.5 Percentages of mothers reporting the receipt of WIC vouchers for formula and supplemental foods	27	Will not repeat. Replaced by table on food packages
Table II.6 Percentages of mothers reporting receipt of information about various aspects of infant feeding from WIC	28	Will repeat
CHAPTER III: CONCEPTUAL MODEL AND APPROACH TO ANALYSIS		
Table III.3 WIC-IFPS data on infant feeding practices in the nursing phase	31	Will not repeat but rather replace with a discussion of the variables we will collect
Table III.2 WIC-IFPS data on infant feeding practices in the transitional phase	33	Will not repeat but rather replace with a discussion of the variables we will collect
Figure III-1 A general model of infant feeding practices and the measures of predictors of infant feeding practices from WIC-IFPS	38	Will replace with graphics of updated model
CHAPTER IV: CHOICE BETWEEN BREASTFEEDING AND FORMULA FEEDING		
Figure IV.1 A model of breastfeeding initiation and the measures of its predictors available from the WIC-IFPS	46	Will replace with graphics of updated breastfeeding decision model
Table IV.1 Breastfeeding initiation rates by selected socio-demographic and health-related characteristics	53	Will repeat
Figure IV.2 Breastfeeding initiation rates, by race and ethnicity of the mother	54	Will repeat
Table IV.2 Estimates of the relative odds estimated by the logistic regression model of breast feeding initiation	58	Will repeat similar content but models will differ

Table A-1. List of WIC-IFPS-1 report tables and figures (continued)

Table/Figure	Page	Status
Figure IV.3 Relative odds of initiating breastfeeding for WIC mothers who received breastfeeding information and advice from different sources	63	Will repeat similar content but specific categories for sources of information will differ
Table IV.3 Items that constitute the perceived benefits of breastfeeding and perceived barriers to breastfeeding scales (factor analysis)	71	Will repeat applying factor analysis but the items will differ
Table IV.4 Percentage of mothers agreeing with the nine statements about perceived benefits of breastfeeding	73	Will repeat but the items will differ
Table IV.5 Percentage of mothers agreeing with the 13 statements about perceived barriers to breastfeeding	74	Will repeat but the items will differ
Figure IV.4 A model of initiation of formula supplementation and the measures of the predictors available from the WIC-IFPS	82	Will replace with graphics of updated breastfeeding duration model
Figure IV.5 Percentages of only breastfeeding, combined breast-and formula feeding, and only formula-feeding WIC mothers at each month of interview	88	Will repeat
Table IV.6. Percentage distribution of the infants by nursing diets at the at the time of each interview month; by selected socio-demographic characteristics	90	Will repeat
Figure IV.6 Percentages of breastfeeding WIC mothers, by type of breastfeeding practice at each month of interview	92	Will repeat
Figure IV.7 Percentage of breastfeeding WIC mothers who have not yet initiated formula, by the age of the infant	94	Will repeat
Table IV.7 Median age in days of the infant at the time when formula supplementation is initiated, by selected socio-demographic characteristics	94	Will repeat but measure child's age in weeks not days
Table IV.8 Estimates of the relative risk estimated by the multivariate models of rates of formula supplementation (survival analysis)	96	Will repeat similar content but models will differ
CHAPTER V:HOSPITAL PRACTICES AND NEONATAL CIRCUMSTANCES EXPERIENCE BY MOTHERS		
Figure V.1 A model of feeding practices at hospital discharge and the measures of its predictors available from the WIC-IFPS	103	Will replace with graphics of updated breastfeeding decision model (for hospital)
Figure V.2 Number of days of hospital stay for WIC mothers and infants	109	Will repeat
Figure V.3 Percentage of WIC infants who stayed in the nursery overnight	109	Will repeat
Table V. 1 The first feeding received by WIC infants in the hospital	110	Will repeat
Figure V. 4 The first feeding of WIC infants in the hospital, by race and ethnicity of the mother	111	Will repeat
Table V.2 Percentages of mothers reporting nursing problems while in the hospital	113	Will repeat
Figure V.5 Percentage of WIC mothers who did not receive help from the hospital staff among those who had common nursing problems	114	Will repeat
Figure V.6 Percentage of WIC mothers who reported receiving	115	Will repeat

Table A-1. List of WIC-IFPS-1 report tables and figures (continued)

Table/Figure	Page	Status
various items in their gift packages from the hospital		

Table A-1. List of WIC-IFPS-1 report tables and figures (continued)

Table/Figure	Page	Status
Table V.3 Percentage of type of feeding at hospital discharge by type of first feeding	116	Will repeat
Table V.4 Relative odds of formula feeding at hospital discharge for WIC mothers who breastfeed at the first feeding	118	Will repeat similar content but models will differ
Table V.5 Relative odds of breastfeeding at hospital discharge for WIC mothers who formula feed at the first feeding	120	Will repeat similar content but models will differ
CHAPTER VI: BREASTFEEDING AND FORMULA FEEDING PRACTICES		
Figure VI.1 A model of daily number of breastfeeds at Month 1 interview and its predictors available from the WIC-IFPS	126	Will not repeat as not deemed to be highly critical outcome
Table VI.1 Breastfeeding schedules of WIC mothers over the first five months of their infants' first year	128	Will repeat
Figure VI.2 Percentage of WIC mothers who breast feed on a set schedule, when the infant cries or seems hungry, and on a mixed schedule	130	Will repeat
Table VI. 2 Usual number of daily breastfeeds, by selected maternal socio-demographic characteristics	131	Will repeat
Table VI.2Percentage of WIC mothers who report expressing milk during the past week, by selected maternal socio-demographics	132	Will repeat
Figure VI.3 Percentage of breastfeeding WIC mothers expressing milk, using electric breast pumps, using manual breast pumps, and expressing milk by hand	133	Will repeat (excluding type of pump)
Table VI.4 Relative contribution of selected non-program and program factors to the usual number of daily breastfeeds reported at Month 1 interview	135	Will repeat similar content but models will differ
Table VI.5 Percentage of WIC mothers who add other foods or liquids into the bottle with the formula by selected socio-demographic characteristics	141	Will repeat
Figure VI.4 Percentage of mothers who report adding other foods or liquids in the bottle with the formula at Month 3	142	Will repeat
Figure VI.4 Percentage of mothers who report adding other foods in the bottle with formula at Month 1 among those who think that the amount of formula given by WIC is more than enough, the right amount, or not enough	143	Will repeat
Table VI.5 Percentage distribution of formula-feeding WIC mothers by brand name of formula	145	Will repeat
CHAPTER VII: FEEDING PROBLEMS, CONTINUATION AND CESSATION OF BREASTFEEDING		
Table VII.1 Reported nursing problems by WIC mothers at the time of the Month 1, Month 3 and Month 5 interviews	153	Will repeat
Figure VII.1 Percentage of breastfeeding WIC mothers who report experiencing nursing problems in Months 1,3 and 5	154	Will repeat
Table VII.2 Median age of breastfeeding cessation, age when 25% and age when 75% of the infants are weaned from the breast	163	Will not repeat; similar information can be better displayed in a graphic

Table A-1. List of WIC-IFPS-1 report tables and figures (continued)

Table/Figure	Page	Status
Figure VII.3 Percentage of all WIC mothers breastfeeding, by age of the infant	164	Will repeat But infant age will not be in days
Figure VII.4 Percentage of all WIC mothers still breastfeeding, by age of the infant and age of the mother	165	Will repeat But infant age will not be in days
Figure VII.5 Percentage of all WIC mothers still breastfeeding, by age of the infant and whether the mother reports knowing about the special WIC food package for breastfeeding women who do not accept infant formula for WIC	166	Will repeat But infant age will not be in days
Table VII.3 Relative risks estimated by the multivariate models of rates of breastfeeding cessation (survival analysis)	168	Will repeat similar content but models will differ
Figure VII.6 Percentage of WIC mothers still breastfeeding by age of the infant and reported receipt of none, one, two, or three WIC program components that support breastfeeding	173	Will repeat But infant age will not be in days
CHAPTER VIII: INITIATION OF SUPPLEMENTAL FOODS: THE TRANSITIONAL PHASE OF INFANT FEEDING		
Figure VIII.1 A model of early initiation of supplemental foods and the measures of its predictors from the WIC-IFPS	180	Will replace with graphics of updated introduction of other foods model
Figure VIII.2 Percentage of WIC mothers who have not yet initiated cereals, vegetables, and meats at each age of the infant	186	Will repeat But infant age will not be in days
Figure VIII.3 Percentage of WIC mothers who have not yet initiated dairy foods, high-protein foods other than meats, and sweet/snack foods, at each age of the infant	188	Will repeat (food categories may differ) But infant age will not be in days
Table VIII.1 Median age of the infant (in days) when specific supplemental foods are initiated by selected socio-demographic characteristics of the mother	189	Will repeat But infant age will not be in days
Figure VIII.4 Percentage of WIC mothers who have not yet initiated cereals at each age of the infant, by maternal immigrant status	190	Will repeat But infant age will not be in days
Figure VIII.5 Percentage of mothers initiating cereals, fruits, vegetables, and meats as the first, second, third or fourth type of supplemental food	192	Will repeat
Table VIII.2 Percentage distribution of the order of initiation of cereals, fruits, vegetables, and meats, by race/ethnicity of the mother	194	Will repeat
Table VIII.3 Relative risk of initiating cereals prior to four months of age	196	Will repeat similar content but models will differ
Table VIII.4 Relative risk of initiating fruits prior to four months of age	199	Will repeat similar content but models will differ
Table VIII.4 Relative risk of initiating fruits prior to four months of age	201	Will repeat similar content but models will differ
Figure VIII.6 Percentage of WIC mothers who have not yet initiated fruit juices, sweet drinks, and cow milk or other milk at each age of infant	207	Will repeat
Table VIII.6. Median age of the infant at the time of initiation of fruit juices or sweet drinks by selected socio-demographics	208	Will repeat
Figure VIII.7 Percentage of WIC mothers who have not yet sweet drinks at each age of infant, by race/ethnicity of the mother	209	Will repeat
CHAPTER IX SUPPLEMENTAL FOOD FEEDING PRACTICES		

Table A-1. List of WIC-IFPS-1 report tables and figures (continued)

Table/Figure	Page	Status
Table IX.1 WIC-IFPS interview months when questions on the method of feeding supplemental foods were elicited	214	Will not repeat as we focus on the dates changes occurred and not the timing of the interview to get behavioral changes information
Table IX.1 Methods of feeding supplemental foods at interview months when data was elicited	215	Will repeat
Figure IX.1 Percentage of WIC infants receiving supplemental foods using a spoon at interview months 2, 4, 5 and 9 by race and ethnicity of the mother	216	Will repeat
Figure IX.2 Percentage of WIC mothers who have used an infant feeder sometime during infancy by race and ethnicity of the mother	217	Will repeat
Table IX.3 Percentage of WIC mothers who adopt supplemental food feeding practices that are generally not recommended	218	Will repeat Rule changes?
Figure IX.3 Percentage of WIC mothers who feed supplemental foods before month 4, prior to using a spoon, by race and ethnicity of the mother	220	Will repeat

This page left intentionally blank

# Appendix B

## Proposed Analyses for Answering Each Research Question

Table B-1 shows which analyses answer each research questions and whether the analysis is repeated from a past study or new. In cases in which the analyses repeats work from past studies we provide the study reference and page number for the relevant table or figure.

**Table B-1. Tabular presentation of research design**

Research question	Analysis and format	Repeated or new
1: What is the participant's practice on breastfeeding and formula feeding her infant?	
Table: Breastfeeding initiation rates by selected socio-demographic and health-related characteristics (Cumulative, Months 1,3)
 
Figure: Breastfeeding initiation rates, by race and ethnicity of the mother (Cumulative, Months 1, 3)
 
Figure: Percentages of only breastfeeding, combined breast-and formula feeding, and only formula-feeding WIC mothers at each month of interview (Months 1-13)
 
Table: Percentage distribution of the infants by initial diets at the at the time of each interview month; by selected socio-demographic characteristics (Months 1, 3)
 
Table:(Model) Estimates of the relative odds estimated by the logistic regression model of breastfeeding initiation (Cumulative, Months 1,3)
 
Table:(Model) Estimates of the relative risk estimated by the multivariate models of rates of formula supplementation (survival analysis) (Months 1-13)
 
Table.(Model) Relative risks estimated by the multivariate models of rates of breastfeeding cessation (survival analysis) (Months 1-13)
	Repeated from IFPS pages53, 54,88, 90, 58,96, 168

 IFPS refers to Baydar, et al. Final Report: WIC Infant Feeding Practice Study, November 1997.

FITSa refers to Seiga-Riz, Anna Marie et al. Food Consumption Patterns of Infants and Toddlers: Where are we Now? in the *Supplement to the Journal of the American Dietetic Association*, 2010.

FITSc refers to Devaney, Barbara et al. Nutrient Intakes of Infants and Toddlers in the *Supplement to the Journal of the American Dietetic Association*, 2004

FITSc refers to Skinner, Jean D. et al. Meal and Snack Patterns of Infants and Toddlers in the *Supplement to the Journal of the American Dietetic Association*, 2004

FITSD refers to Ponza, Michael et al. Nutrient Intakes and Food Choices of Infants and Toddlers and Toddlers Participating in WIC in the *Supplement to the Journal of the American Dietetic Association*, 2004

FITSe refers to Carruth, Betty Ruth et al. Developmental Milestones and Self-Feeding Behaviors in Infants and Toddlers in the *Supplement to the Journal of the American Dietetic Association*, 2004

**Table B-1. Tabular presentation of research design (continued)**

Research question	Analysis and format	Repeated or new
1a: Does the practice/behavior correspond to specific past feeding experiences (cultural norms, support received, personal feelings, barriers encountered, etc.)?	
Table: Items that constitute the perceived benefits of breastfeeding and perceived barriers to breastfeeding scales (factor analysis) (Prenatal)
 
Table: Percentage of mothers agreeing with statements about perceived benefits of breastfeeding by breastfeeding decision (Prenatal)
 
Table: Percentage of mothers agreeing with the statements (Prenatal) about perceived barriers to breastfeeding by breastfeeding decision
 
Table: Percentage of mothers receiving breastfeeding education/support (WIC vs. elsewhere) by breastfeeding decision (Cumulative; Months 1,3)
 
Same as breastfeeding initiation model above
	
Repeated from IFPS pages 71, 73, and 74
 
Last table is new

1b: How does breastfeeding advice or support compare to rates of initiation, duration and exclusivity of breastfeeding?	
Figure: (Model) Predicted relative odds of initiating breastfeeding for WIC mothers who received breastfeeding information and advice from different sources (Cumulative; Months 1,3)
 
Same as last table above and formula supplementation and breastfeeding cessation models in question 1
	
Repeated from IFPS, page 63 but use different categories

1c: Are differences from one re-interview to the next statistically significant?	
Figure : Percentages of breastfeeding WIC mothers, by type of breastfeeding practice at each month of interview (Month 1-9)
 
Figure: Percentage of breastfeeding WIC mothers who have not yet initiated formula, by the age of the infant (Months 1-9)
	
Repeated from IFPS, pages 92 and 94

2: What is the frequency of breastfeeding or formula feedings and foods (total and by breast, formula, combinations, and foods) given?	
Table : Usual number of daily breastfeeds, by selected maternal socio-demographic characteristics (Months 1, 3, 5)
 
Table: Usual number of formula or combination feedings, by selected maternal socio-demographic characteristics (Months 1, 3, 5)
 
Table: Usual number of solid food feedings , by selected maternal socio-demographic characteristics (Months 1, 3, 5)
	
Repeated from IFPS, pages 131
 
2nd and 3rd tables are new

2a: Do mothers/caregivers ever put anything other than human milk or formula in a bottle that is fed to their infant?	
Table: Percentage of WIC mothers who add other foods or liquids into the bottle with the formula by selected socio-demographic characteristics (Months 1,3)
 
Figure: Percentage of mothers who report adding other foods or liquids in the bottle with formula at months 3 (Month 3)
 
Figure: Percentage of mothers who report adding other foods in the bottle with formula at Month 1 among those who think that the amount of formula given by WIC is more than enough, the right amount, or not enough (Month 1)
	
Repeated from IFPS, pages 141, 142, 143

3: What is the mean and range in the incidence, duration, and intensity of breastfeeding? Not collecting duration of individual breastfeeds	
Table: Mean and standard deviation in the number of breastfeeds and intensity (% of feedings that are breast feedings) per day by month (Months 1-7)
	
New

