## 7.2 Key Analytical Variables

### ***Outcomes and Key Feeding Decisions***

To answer the research questions and update past analyses, we will assess feeding practice decisions, child nutrient and food intake, and weight outcomes. As the variety of foods infants consume is very limited in the initial months of a child’s life, the feeding practices the caregiver employ are key to nutrient intake. In contrast, once the child is eating a variety of foods, direct food intake measures become the most important measures of dietary quality. The main feeding practice decisions and outcomes are listed below. All variables will be examined by frequencies and how they vary by key

socio-demographics, however, only those that are not italicized will be used as outcomes in the causal model estimations.

- **Breastfeeding Decisions.** *Intent to breastfeed*, initiation of breastfeeding, *first hospital feeding*, breastfeeding at hospital discharge
- **For Those Who Breastfeed.** *Use of breast pump*, time until formula supplementation, time until breastfeeding cessation
- **Other Infant Feeding Practices.** *Number of feedings per day*, time until cereal, time until baby foods (by type), *duration of bottle use*, *timing of feeding transition*
- **Nutrient Intake and Weight Outcomes.** *Foods eaten by type*, *calorie intake per kilogram of body weight*, *usual nutrient intakes relative to Estimated Requirements (EARs) (where these exist and Adequate Intakes (AIs) otherwise)*, *nutrient densities*, *nutrient intakes relative to UL (where these exist)*, *weight-for-length*, *weight/length gain (0-6 months)*, *weight/length gain (6-12 months)*.

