Figure: Percentages of only breastfeeding, combined breast-and formula feeding, and only formula-feeding WIC mothers at each month of interview (Months 1-13)	IFPS-1 p88	Both
Table: Transitions of Mother's Food Package Issued by Age of Infant (Months 1, 3)	WBM, p100	Core
Table: Percentage distribution of the perceived impact of food package choice on the breastfeeding decision (Months 3, 7)	New	Both
Table: Percentage distribution of the infants by initial diets at the time of each interview month; by selected socio-demographic characteristics (Months 1, 3)	IFPS-1 p90	Both
Table: Usual number of formula or combination feedings, by selected maternal socio-demographic characteristics(Months 1, 3, 5)	New	Both
Table: Usual number of solid food feedings , by selected maternal socio-demographic characteristics (Months 1, 3, 5)	New	Both
Figure:: Percentages of breastfeeding WIC mothers, by type of breastfeeding practice at each month of interview (Months 1-9)	IFPS-1 p92	Both
Figure: Percentage of breastfeeding WIC mothers who have not yet initiated formula, by the age of the infant (Months 1-9)	IFPS-1 p94	Both

Table 7-2. Summary of analyses to be conducted (continued)

Table/Figure (Interview months)	Source	Sample
Formula Supplementation (continued)		
Table: Breastfeeding frequency, intensity, and duration by initial breastfeeding status (breastfeed only or with formula) (Months 1, 3, 5, 7)	New	Both
Table: Intensity of Breastfeeding, Overall (Month 1)	WBM, p126	Both
Table; Intensity of Breastfeeding, by Mother's Food Package (Month 1)	WBM, p127	Both
Table: Median age in weeks of the infant at the time when formula supplementation is initiated, by selected socio-demographic characteristics and previous breastfeeding experience (Cumulative; Months 1-13)	IFPS-1 p94	Both
Table: (Model) Estimates of the relative risk estimated by the multivariate models of rates of formula supplementation (survival analysis) (Months 1-13)	IFPS-1 p96	Both
Breastfeeding and Formula Feeding Practices		
Table: Breastfeeding schedules of WIC mothers over the first five months of their infants' first year (Months 1, 3, 5)	IFPS-1 p128	Both
Table: Breastfeeding schedules of WIC mothers over the first 13 months of their infants' first year by mother's work status and child care status (Months 1-13)	New	Both
Figure: Percentage of WIC mothers who breast feed on a set schedule, when the infant cries or seems hungry, and on a mixed schedule (Months 3-13)	IFPS-1 p130	Both

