**Table 7-3. Proposed model specifications**

Model	Dependent variable	Estimation methods	Minimum covariates to explore
Breastfeeding decision	
 
■ Initiating breastfeeding
 
■ Breastfeeding at hospital discharge
 
 Measured dichotomously and categorically (all breastfeeding, combination, all formula)	
 
■ Logistic regression (dichotomous)
 
■ Multinomial logistic regression (categorical)
 
	
 
■ Socio-demographics: Age, race/ethnicity, born in US, father in house, infant first born, income, poverty level, education, worked during pregnancy
 
■ Maternal and infant health: Mother's post-delivery health status, infants health status (measured as in NICU or more than 6 weeks premature or very low birth weight)
 
■ Prenatal attitudes, beliefs and knowledge: Perceived benefits of breastfeeding, perceived barriers, breastfeeding intentions
 
■ Prenatal experience and advice: breastfed previous children, receipt of advice to breastfeed from physician, receipt of advice to breastfeed from family, receipt of breastfeeding information from non-WIC sources
 
■ WIC program experience: Education, peer counseling, time in WIC
 
■ Hospital experience: Mom's length of stay, baby's length of stay, receipt of formula or bottle in gift package, had baby friendly practices
 

Table 7-3. Proposed model specifications (continued)

Model	Dependent variable	Estimation methods	Minimum covariates to explore

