Formula Supplementation	
 
■ Time until formula supplementation
 
	
 
■ Survival analysis
 
	
 
■ Socio-demographics: Age, race/ethnicity, born in US, infant first born, use of childcare, education, worked during pregnancy
 
■ Maternal and infant health: Mother's post-delivery health status, infants health status, birth weight, reported problems breastfeeding
 
■ Prenatal attitudes, beliefs and knowledge: Perceived benefits of breastfeeding, perceived barriers, how long intend to breastfeed
 
■ Prenatal experience and advice: Receipt of advice to breastfeed from physician, receipt of breastfeeding information from non-WIC sources
 
■ WIC program experience: Education, peer counseling, breast pumps, time in WIC
 

Breastfeeding cessation	
 
■ Time until cessation
 
	
 
■ Survival analysis
 
	
 
■ Socio-demographics: Age, race/ethnicity, born in US, infant first born, education, use of child care
 
■ Maternal health: Reported breastfeeding problems
 
■ Breastfeeding practices: Current use of formula
 
■ Prenatal attitudes, beliefs and knowledge: Perceived benefits of breastfeeding, perceived barriers, how long intend to breastfeed
 
■ Prenatal experience and advice: Receipt of advice to breastfeed from physician, receipt of breastfeeding information from non-WIC sources
 
■ WIC program experience: Education, peer counseling, breast pumps, time in WIC
 
■ Return to work/school: Returned to work/school within 2 months
 

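### Question 1b asks how advice relates to exclusive breastfeeding, but after hospital discharge its mapped analyses measure only formula avoidance

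*Combined protocol and SAP*

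**What the plan says.** Question 1b in Table B-1 names three outcomes: "How does breastfeeding advice or support compare to rates of initiation, duration and exclusivity of breastfeeding". It is answered with a figure of relative odds of initiation by source of advice and with this entry: "Same as last table above and formula supplementation and breastfeeding cessation models in question 1". The table referred to there, listed under question 1a, shows receipt of education or support by breastfeeding decision.

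The outcomes behind these entries are set out in two places:

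- Section 7.2 lists, for mothers who breastfeed, the model outcomes "time until formula supplementation, time until breastfeeding cessation". No outcome is called exclusive breastfeeding.
- Table 7-3 gives the formula model the dependent variable "Time until formula supplementation". Its advice covariates are "Receipt of advice to breastfeed from physician, receipt of breastfeeding information from non-WIC sources", with WIC education, peer counseling, breast pumps and time in WIC as program covariates.

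The breastfeeding decision model in Table 7-3 covers initiation and hospital discharge. Its outcome is "Measured dichotomously and categorically (all breastfeeding, combination, all formula", and advice from physician and family is among its covariates.

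Monthly feeding status is reported as "Percentages of only breastfeeding, combined breast-and formula feeding, and only formula-feeding WIC mothers at each month of interview (Months 1-13" (Table 7-2, repeated in Table B-1 under question 1).

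**The concern.** Initiation and duration each have a matching analysis under 1b. Exclusivity after discharge does not; it is left to a model whose event is formula. An infant who is breastfed, has had no formula and has been given cereal or juice has not had that event.

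The plan itself expects such infants. Table 7-2 models cereals, fruits and vegetables begun before four and before six months, and tabulates solid-food feedings at Months 1, 3 and 5.

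At stake is what 1b can claim. One of the study's primary objectives (Section 1.1) is to judge education and breastfeeding promotion against recommended feeding patterns, and the plan undertakes to answer all 60 questions. As mapped, 1b would report an association of advice with avoiding formula. The monthly label 'only breastfeeding', carried to Month 13 and set against formula categories alone, invites the reader to take this as exclusivity.

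**Working it through.** The plan states no figure for this analysis, so there is nothing to reproduce. The check compares the question with the outcomes and then works out the direction and possible size of the gap.

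**Step 1. Where advice meets an outcome.**

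| Analysis | Outcome | Advice or program covariates | Mapped to 1b? | Exclusivity after discharge? |
|---|---|---|---|---|
| Decision model (Table 7-3) | Initiation; feeding at discharge, two-way or three-way | Physician, family, non-WIC information, WIC education, peer counseling | Initiation odds only | No, stops at discharge |
| Formula model | Time to formula | Physician, non-WIC information, WIC education, peer counseling, pumps | Yes | Formula component only |
| Cessation model | Time to end of any breastfeeding | Physician, non-WIC information, WIC education, peer counseling, pumps | Yes | No |
| Other-foods models | Time to cereal, fruits, vegetables, meats, each alone | Non-WIC information, WIC education | No | Not limited to breastfed infants; not combined with formula |
| Juice, sweet drinks, other milk (Table 7-2) | Share not yet started | None; descriptive | No | No |

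No row has an event that ends at the first feed other than breast milk.

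**Step 2. Direction.** Let T_formula be age at first formula and T_other be age at first other food or drink. Exclusive breastfeeding ends at min(T_formula, T_other), which is never later than T_formula. Time to formula therefore equals or exceeds the exclusive duration for every infant.

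**Step 3. Size of a prevalence gap (assumed inputs).** Let S be the share breastfed and formula-free at a given age, and q the fraction of those already given another food or drink. Neither is in the documents. Then the exclusive share is S × (1 − q) and the gap is S × q.

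- S = 30%, q = 5%: 28.5% exclusive, gap 1.5 points.
- S = 30%, q = 20%: 24%, gap 6 points.
- S = 30%, q = 50%: 15%, gap 15 points.
- S = 30%, q = 80%: 6%, gap 24 points.
- Extremes over S = 20% to 40% and q = 5% to 80%: 0.20 × 0.05 = 1 point, and 0.40 × 0.80 = 32 points.

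The gap is small while few infants have had other foods and grows as q rises.

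**Step 4. Effect on the advice association (assumed inputs).** With constant cause-specific hazards h_f for formula and h_o for other foods, and advice hazard ratios HR_f and HR_o, the hazard ratio for loss of exclusivity is (h_f × HR_f + h_o × HR_o) / (h_f + h_o).

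| h_f, h_o | Other foods' share of hazard | Advice acts on formula only (0.70, 1.00) | On other foods only (1.00, 0.70) | On both (0.70, 0.70) |
|---|---|---|---|---|
| 0.40, 0.05 | 11% | (0.28 + 0.05)/0.45 = 0.73 | (0.40 + 0.035)/0.45 = 0.97 | 0.70 |
| 0.30, 0.10 | 25% | (0.21 + 0.10)/0.40 = 0.78 | (0.30 + 0.07)/0.40 = 0.93 | 0.70 |
| 0.20, 0.20 | 50% | (0.14 + 0.20)/0.40 = 0.85 | (0.20 + 0.14)/0.40 = 0.85 | 0.70 |

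The formula model targets HR_f: 0.70, 1.00 and 0.70 in the last three columns. It matches the exclusivity association when advice acts equally on both hazards. Otherwise it can be too strong (0.70 against 0.85) or miss an effect (1.00 against 0.85).

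**The case against.** A reader might infer that the plan never links advice to exclusivity at all. The documents do not support that. The decision model relates advice to a three-way feeding outcome at initiation and discharge, and the formula model estimates one component of exclusivity over time. Section 7.5 also allows Table 7-2 measures to be broken down by the support received at hospital, home, WIC, work and childcare, where applicable. That could include the monthly feeding figure, breastfeeding intensity, and combination feedings by age. The last is mapped to question 11b, which does count foods. These are descriptive breakdowns not mapped to 1b, and none gives the duration of exclusive breastfeeding.

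A reader might also infer that advice which delays cereal would be invisible. It would not: the other-foods models carry WIC education and non-WIC breastfeeding information. They omit physician advice and peer counseling, cover all infants, and sit outside 1b. Juice, sweet drinks and other milk have no model.

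A third objection is that the plan labels its outcome as formula supplementation and does not call it exclusivity. That is correct. The plan also states no rule for other foods in that model; that they are ignored is read from the outcome's name, and detailed variable definitions sit in a separate Database Plan. Overstatement therefore arises only if the outcome is used to answer the exclusivity part of 1b, which the mapping invites.

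Finally, Section 7.5 keeps these models close to the earlier WIC study on purpose and proposes to explore exclusivity. The first is a good reason to retain the formula model. The second concerns mothers' intentions as the predictor, not advice.

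**Conclusion.** The point holds in a limited form. Followed as written, 1b yields the association of advice with initiation, with formula supplementation and with cessation. It does not yield the association with the duration of exclusive breastfeeding counting all non-breast-milk feeds.

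The direction of the prevalence error is certain if time to formula is read as exclusivity: upward or nil. Its size is unknown. The range of 1 to 32 points rests wholly on assumed values of S and q, and the hazard ratios in the working rest on assumed constant hazards.

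It is tempting to scale the plan's estimate in Section 5.7 that fewer than 15 percent of WIC infants are fully breast-fed. That figure comes from a discussion of breast-milk intake and is not a formula-free rate. If it already excludes infants given other foods, scaling it would remove them twice, so it gives no size for this gap.

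**What to change.** 1. Define exclusive breastfeeding in Section 7.2, listing what ends it. Derive time to its end as the earliest of first formula, other milk, juice or sweet drink, cereal or any other food. Footnote 13 in Section 6.3 says dates for starting formula and supplemental foods are asked until obtained, and Table 7-2 already uses starting ages for juices, sweet drinks and other milk.
2. Add a row to Table 7-3 fitting the formula-supplementation survival model to this outcome, with the same advice and WIC program covariates.
3. Add a table of percent exclusively breastfed at early ages (for example 1, 3, 4 and 6 months) by advice and support received.
4. Map question 1b to both additions, and cross-refer to the three-way discharge analysis.
5. Keep the formula model unchanged for comparison with the earlier study. Relabel 'only breastfeeding' in the monthly figure as 'breastfeeding, no formula'.

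The cost is one derived variable, one model and one table, with no new data collection.
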